4.5.2.2 Serious Adverse Events

The incidences of SAEs will be presented by SOC and PT, and a listing of all SAEs will be presented.

4.5.2.3 Adverse Events Leading to Study Drug Discontinuation

The incidences of TEAEs leading to study drug discontinuation will be presented by SOC and PT, and a listing of AEs that led to discontinuation of study drug will be presented.

4.5.3 Laboratory Data

4.5.3.1 Potentially Clinically Significant Laboratory Values

The number and percentage of subjects with PCS values post-baseline will be summarized for the hematology and chemistry parameters defined in Table 1 and Table 2. All scheduled and unscheduled results will be included in this laboratory analysis.

Hematology parameter	Potentially clinically significant values
Hemoglobin	Female: <85 g/L or >160 g/dL)
	Male: <90 g/L or >170 g/L)
Hematocrit (HCT)	Hematocrit (Female) ≤32% or >49 %
	Hematocrit (Male) ≤37% or >48 %
Platelet count	<125 x 10^9/L or >470 10^9/L
White blood cells (WBC)	<2.0 x 10^9/L or >12.0 10^9/L
Basophils	>0.5 x 10^9/L
Eosinophils	>1.5 x 10^9/L
Lymphocytes	<0.5 x 10^9/L or >6.0 10^9/L
Monocytes	>1.6 x 10^9/L
Neutrophils	<1.5 x 10^9/L

Chemistry parameter	Potentially clinically significant values
Alanine aminotransferase	>3 x upper limit of normal (ULN)
(ALT)	
Albumin	<22 g/L or >65 g/L
Aspartate aminotransferase	>3 x ULN
(AST)	
Alkaline Phosphatase (ALP)	>3 x ULN
Bilirubin	>2 x ULN
Blood urea nitrogen (BUN)	>9.6 mmol/L
Calcium	<2.0 mmol/L or >2.75 mmol/L
Chloride	<90 mmol/L or >120 mmol/L
Creatinine	> 1.3 mg/dL or >115 µmol/L
Potassium	<3 mmol/L or >5.8 mmol/L
Sodium	<125 mmol/L or >158 mmol/L
Protein	<45 g/L
Glucose	non-fasting < 2.2 mmol/L or >8.9 mmol/L

Abnormally low or high laboratory results based on the laboratory normal ranges will be presented in a data listing.

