# 3.3.2.2. Exclusion Criteria 'A'

- 1. Is currently participating in another clinical trial other than Study 812P306.
- Has any current psychiatric disorder per Diagnostic and Statistical Manual of Mental Disorders - 5th Edition (DSM-5) criteria other than ADHD with the following exceptions: ADHD is primary diagnoses with comorbidity/secondary diagnoses of major depression disorder (MDD), nicotine dependence, social anxiety disorder, generalized anxiety disorder, or phobias.
- 3. Current diagnosis of significant systemic disease and/or of a major psychiatric or neurological disorder, including history or family history of seizures or seizure-like disorders.
- 4. Current evidence of suicidality (suicidal thoughts or behaviors).
- 5. Female subjects who are pregnant, lactating and/or sexually active and not agreeing to use one of the acceptable birth control methods throughout the study.
- 6. Has a positive result on urine drug screen at Visit 1.
- 7. Use of prohibited concomitant medications including known CYP1A2 substrates (e.g., theophylline, melatonin) at the Visit 1 for the duration of the study.
- 8. Has a clinical laboratory value, vital sign value or ECG result at Visit 1 that is considered to be clinically significant in the opinion of the Investigator.

- 9. Has one or more clinical laboratory test values outside the reference range at Visit 1 that, in the opinion of the Investigator, are clinically significant, or any of the following (see Note below):
  - Serum creatinine > 1.5 times the upper limit of normal (ULN);
  - Serum total bilirubin > 1.5 times ULN;
  - Serum alanine aminotransferase or aspartate aminotransferase > 2 times ULN.
- 10. Has any of the following cardiology findings at Visit 1 (see Note below):
  - Abnormal ECG that is, in the Investigator's opinion, clinically significant;
  - PR interval > 220 ms;
  - QRS interval > 130 ms;
  - QTcF interval > 450 ms (for men) or > 470 ms (for women) (QT corrected using Fridericia's method);
  - Second- or third-degree atrioventricular block;
  - Any rhythm, other than sinus rhythm, that is interpreted by the Investigator to be clinically significant.
- 11. Any reason that, in the opinion of the Investigator, would prevent the subject from participating in the study.

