3.2 Baseline Values

For all safety assessments, baseline will be defined as the last non-missing value prior to SPN-812 dosing in the 812P311 study.

For all efficacy assessments, subjects enrolled into $812P311 \le 7$ days after their last 812P306 visit, the "baseline" efficacy assessment is defined as the assessment that subject completed at Visit 2 in 812P306 prior to the first dose of SPN-812 in 812P306. Additionally, for subjects enrolled into 812P311 > 7 days after their last 812P306 visit, the baseline efficacy assessment is defined as the assessment that was completed at Visit 1 in 812P311 prior to the first dose SPN-812 in 812P311.

All post-baseline assessments are defined as any assessments that were completed after the first dose of SPN-812 in the 812P311 study.

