4.5.3.2 Abnormal Liver Enzymes and Liver Function Values

Summaries of abnormal liver enzymes and liver function tests post-baseline will be presented for ALT, AST, Direct Bilirubin, Total Bilirubin, and ALP. All scheduled and unscheduled results will be included in these analyses.

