4.5.4 Vital Signs

The number and percentage of subjects with abnormally low or high vital sign values postbaseline based on the normal ranges defined in Table 3 will be presented. All scheduled and unscheduled results will be included in this analysis.

Measurement	Normal Range
Body mass index	$18 - 35 \text{ kg/m}^2$
Temperature	95-100 °F (35-37.8 °C)
Diastolic blood pressure	60 – 90 mmHg
Systolic blood pressure	90 – 140 mmHg
Heart rate	50 – 100 bpm
Respiration rate	10-25 breaths per minute

Table 3 Vital Signs Normal Ranges

A listing of subjects with abnormalities in vital sign parameters will be presented.

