4.5.5 ECG Data

Twelve-lead ECGs will be collected. Descriptive summaries will be presented for heart rate (bpm), PR interval (msec), QRS duration (msec), uncorrected QT interval (msec), and QTcF (msec).

Normal, abnormal but not clinically significant, and abnormal and clinically significant ECG investigator interpretation results will be summarized and flagged in the listings.

The number and percentage of subjects with post-baseline abnormally low or high values for heart rate, PR interval, and QRS duration based on the normal ranges defined in Table 4 will be presented.

Table 4	ECG Normal Ranges	

Parameter	Low	High
Heart Rate (beats/min)	45	120
PR Interval (msec)	120	220
QRS Duration (msec	80	130

Additionally, the number and percentage of subjects with actual QT and QTcF values \leq 450 msec, 450 msec to \leq 480 msec, 480 to \leq 500 msec, >500 msec and with changes from baseline \leq 30 msec, 30 msec to \leq 60 msec, and >60 msec will be presented.

All ECG results will be displayed in the data listings.

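### The post-baseline abnormality counts in SAP 4.5.3.1, 4.5.4 and 4.5.5 are not split by baseline status and no shift table is listed, so persistent and new abnormalities are counted alike

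*SAP*

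**What the plan says.** Three sections of the SAP count subjects whose values fall outside fixed limits after dosing starts.

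- Laboratory (4.5.3.1, Tables 5.1.1 and 5.2.1): "The number and percentage of subjects with PCS values post-baseline will be summarized".
- Vital signs (4.5.4, Table 6.2): "The number and percentage of subjects with abnormally low or high vital sign values postbaseline".
- ECG (4.5.5, Table 7.3): "The number and percentage of subjects with post-baseline abnormally low or high values for heart rate, PR interval, and QRS duration". The same section bands actual QT and QTcF at 450, 480 and 500 msec.

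SAP 3.2 fixes what post-baseline means: "All post-baseline assessments are defined as any assessments that were completed after the first dose of SPN-812 in the 812P311 study". It also defines a safety baseline, the last non-missing value before 812P311 dosing.

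None of the three rules restricts the numerator or denominator by that baseline, requires worsening, or asks for a split. The table list in SAP 5.1 has no shift table. SAP 4.5.3.2 is worded the same way for liver tests ("Summaries of abnormal liver enzymes and liver function tests post-baseline will be presented") but gives no limits, so it is left out of the comparison below.

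Baseline is used elsewhere. SAP 4.5.5 also counts subjects by QT and QTcF category "and with changes from baseline". Tables 5.1.2, 5.2.2 and 5.4 give laboratory change from baseline by visit, and Protocol 7.9 plans change from baseline for laboratory values and vital signs.

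**The concern.** Laboratory tests, vital signs and ECGs are among the primary safety endpoints, and the study has no comparator. When a table says that a given percentage of subjects had a diastolic pressure above 90 mmHg after baseline, the reader's main protection against taking a long-standing trait for a new event is the subject's own baseline. The SAP defines that baseline, but these four tables do not show it for the fixed-limit counts. Mean change by visit does not fill the gap, because a mean does not show who crossed a limit. Heart rate, PR, QRS and the vital signs have no outlier count that refers to baseline.

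Follow-up makes this more pressing. Protocol 3.1 schedules Visits 2 to 22, and the laboratory and vital-sign counts also take in unscheduled results. A subject outside a limit at entry has many chances to be outside it again.

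**Working it through.** The plan states no abnormality rate, sample-size calculation or power, so there is no figure of its own to reproduce. The check has three steps.

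**Step 1. Can a subject enter already outside a reporting limit?** Entry limits are from Protocol 3.3.2.2 and 3.3.3.2, reporting limits from SAP 4.5.3.1, 4.5.4 and 4.5.5.

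| Measure | Reporting limit | Numeric entry limit | Overlap |
|---|---|---|---|
| Creatinine | >115 µmol/L | "Serum creatinine > 1.5 times the upper limit of normal (ULN") excluded | Yes, if ULN exceeds 76.7 µmol/L |
| QTcF, women | bands above 450 ms | >470 ms excluded | Yes, 450 to 470 ms |
| Blood pressure | outside 60–90 / 90–140 mmHg | none (clinical significance only) | Yes |
| Hematocrit | ≤32% or >49% (F), ≤37% or >48% (M) | none (clinical significance only) | Yes |
| PR low, QRS low | <120 ms, <80 ms | none (clinical significance only) | Yes |
| QTcF, men | bands above 450 ms | >450 ms excluded | No |
| PR high, QRS high | >220 ms, >130 ms | same values excluded | No |
| ALT/AST | >3 x ULN | >2 x ULN excluded | No |
| Bilirubin | >2 x ULN | >1.5 x ULN excluded | No |

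The QTcF criterion reads "QTcF interval > 450 ms (for men) or > 470 ms (for women"). For creatinine, 115 / 1.5 = 76.7 µmol/L, or 76.7 / 88.4 = 0.87 mg/dL. The two PCS limits agree with each other: 1.3 mg/dL x 88.4 = 114.9 µmol/L. Criteria B apply the limits at screening, up to 28 days before Visit 1, so a No in the table means largely excluded, not impossible.

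**Step 2. What the rule counts.** Let q be the share outside the limit at baseline, r the share of those outside it again after dosing, and e the rate of new abnormality among the rest. None of these is in the documents; all are assumed.

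- Subjects counted under the SAP = N x [q x r + (1 − q) x e]
- New cases = N x (1 − q) x e, out of N x (1 − q)
- Share already outside = q x r / [q x r + (1 − q) x e]

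With N = 366 (the maximum) and e = 5%:

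| q | r | SAP count | New cases | Share already outside |
|---|---|---|---|---|
| 0% | any | 18.3 (5.0%) | 18.3 / 366 | 0% |
| 2% | 50% | 21.6 (5.9%) | 17.9 / 358.7 | 17% |
| 5% | 90% | 33.9 (9.3%) | 17.4 / 347.7 | 49% |
| 10% | 100% | 53.1 (14.5%) | 16.5 / 329.4 | 69% |

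For q = 5% and r = 90%: 366 x (0.045 + 0.0475) = 33.9, and 0.045 / 0.0925 = 49%. Pre-existing cases add N x q x r. At q = 5% that is 0 to 18.3 subjects as r runs from 0 to 100%.

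**Step 3. How large r may be over repeated visits.** This is a simulation of 200,000 subjects with normal between- and within-subject components, no drug effect, and a baseline plus 6 or 21 post-baseline visits. Means and SDs are assumed. The schedule gives 21 post-baseline visits for vital signs and 20 for ECG.

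| Measure (mean; between SD, within SD) | Counted | Of these, already outside | Rate among subjects inside at baseline |
|---|---|---|---|
| Diastolic >90 mmHg (77; 8, 6) | 27–42% | 22–29% | 21–37% |
| QRS <80 ms (92; 9, 3) | 19–24% | 41–52% | 10–16% |
| QTcF >450 ms, women eligible to 470 (420; 16, 9) | 13–21% | 21–29% | 10–18% |

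In these runs q is about 5% to 10% and r about 80% to 98%. Moving the assumed QRS mean from 92 to 98 ms cuts the share counted to about 6–9%, of whom 31–42% were already outside.

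**The case against.** The strongest reply is that the counts are over-inclusive on purpose. In a safety study that is the cautious direction, and removing subjects abnormal at baseline could do harm. For Schedule A subjects, Protocol 3.1 makes the 812P306 end-of-study assessment the Visit 1 assessment, so for anyone treated with SPN-812 there, the 812P311 baseline may be on drug. An abnormality that began in 812P306 would disappear from a count restricted to in-range baselines. This stands, and it rules out restricting the count.

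Three stronger readings are tempting, and the documents do not support them.

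- A reader might infer that every subject outside a limit before dosing is counted. That is not so: a value outside the limit after the first 812P311 dose is required.
- A reader might infer that the SAP ignores baseline. It does not. A woman who enters at 465 ms and stays there falls in the QTcF change category of 30 msec or less. That covers QTcF in part, though it does not show who moved between absolute bands.
- A reader might infer that the tables present old abnormalities as drug effects. Tables 5.1.1 and 5.2.1 are titled as post-baseline results, and 6.2 and 7.3 as abnormalities; none says treatment-emergent.

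Other points also carry weight. Inclusion Criterion A2 requires clinically normal results in the investigator's opinion, and Criteria B hold BMI to the same 18 to 35 kg/m² range as SAP Table 3. Full listings are planned, so the split could be rebuilt by hand. The table shells in Appendix B of the SAP were not available, and a baseline row there cannot be excluded. Finally, much of the simulated 27–42% for diastolic pressure comes from repeated measurement, which a baseline split does not remove.

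**Conclusion.** The point holds as a gap in presentation with real consequences for interpretation. As written, Tables 5.1.1, 5.2.1, 6.2 and 7.3 cannot separate a persistent abnormality from a new one, and no other listed table does so for the fixed limits. It applies mainly to creatinine, female QTcF between 450 and 470 ms, blood pressure, hematocrit, short PR and narrow QRS. For ALT/AST, bilirubin, high PR, high QRS and male QTcF, the entry criteria leave little room for it.

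The size cannot be fixed from the documents. Under the assumed distributions, roughly 20% to 50% of flagged subjects were already outside the limit at baseline. The share is zero if no baseline abnormality recurs, and it changes with the assumed means and SDs. These figures show that the mixing may be material; they do not predict this trial's results. The change is worth making before the tables are run.

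**What to change.** In SAP 4.5.3.1, 4.5.4 and 4.5.5, keep the present count of subjects with any post-baseline value outside the limit. Add to Tables 5.1.1, 5.2.1, 6.2 and 7.3 a split by baseline status: inside the limit, outside the limit, missing. Give each row its own denominator of subjects in that row with at least one post-baseline value. A shift table of baseline category by worst post-baseline category would serve equally well. For QTcF, use each subject's maximum post-baseline band against the baseline band.

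Do not drop subjects who are abnormal at baseline. Show the split also by prior 812P306 treatment (SPN-812, placebo, none), so that an abnormality already present on SPN-812 at entry remains visible.

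The cost is a few more rows in four tables, a short change to the SAP text, and the 812P306 treatment assignment as a grouping variable. No new data need to be collected from subjects.

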# 7.10. Sample Size and Power Considerations

There is no consideration for power or sample size determination in this open label study. The present study is an extension of the blinded 812P306 study in patients with ADHD.

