2.6.3 Laboratory Evaluations

Laboratory tests will include hematology, serum chemistry, and urinalysis. Values will be presented using the international system of units (SI).

Hematology:

Hematology parameters will include complete blood count (CBC), white blood cell count with differential, platelet count, red blood cell (RBC) count, hemoglobin, and hematocrit.

Serum Chemistry:

Serum chemistry parameters will include albumin, alanine aminotransferase (ALT), aspartate aminotransferase (AST), alkaline phosphatase (ALP), bicarbonate, bilirubin (direct), bilirubin (total), blood urea/blood urea nitrogen (BUN), calcium, chloride, creatinine, phosphate, potassium, sodium, total protein, and glucose.

Urinalysis:

Urinalysis parameters will include bilirubin, glucose, ketones, nitrites, occult blood, pH, protein, specific gravity, urobilinogen, and WBCs.

Other:

Serology, follicle stimulating hormone (FSH), serum drug screen results, standard urine drug screen results, point of care urine drug screen results, and pregnancy test results will be listed separately.

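### The upper potentially clinically significant limit for female haemoglobin is written in g/dL instead of g/L, so the high side of the rule, coded as written, cannot flag any woman

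*SAP*

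**What the plan says.** SAP section 4.5.3.1 sets sex-specific PCS limits for haemoglobin. For women it gives "Female: <85 g/L or >160 g/dL"; for men, "Male: <90 g/L or >170 g/L". The haematocrit row that follows also has separate limits by sex, starting with "Hematocrit (Female) ≤32% or >49" per cent for women.

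The limits have one stated use: "The number and percentage of subjects with PCS values post-baseline will be summarized for the hematology and chemistry parameters" defined in the section's tables. The hematology output is Table 5.1.1 in the SAP list of tables.

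On units, SAP section 2.6.3 says: "Values will be presented using the international system of units (SI"). No other section restates or corrects the female haemoglobin limit. Protocol section 7.9 gives no PCS limits, and Protocol section 7.1 lets the SAP's methods override its own. The SAP table is therefore the only place in these documents where a programmer can find the rule.

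**The concern.** Two units stand in one cell: g/L for the low limit and g/dL for the high limit. This limit decides which subjects are counted, so the slip is more than cosmetic. If it is followed literally, the high-haemoglobin count for women is fixed at zero before any data are seen. A reader of Table 5.1.1 could not tell that zero from a true absence of high values, and the high-side results for men and women would not be comparable. Laboratory results are among the primary safety endpoints (Protocol section 2.3), so the rule should be correct before it is programmed.

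**Working it through.** **Inputs from the SAP.** Female limits: 85 g/L (low) and 160 g/dL (high). Male limits: 90 g/L and 170 g/L. Female upper haematocrit limit: 49%.

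**Inputs assumed (not in the documents, used only to judge plausibility).** Whole-blood density 1040–1070 g per litre; haemoglobin concentration within red cells 300–380 g/L.

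The SAP derives none of these limits, so there is no calculation of its own to reproduce.

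1. **Conversion.** 1 g/dL = 10 g/L, so 160 g/dL = 160 × 10 = 1600 g/L.

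2. **Against the neighbouring limits.** 1600 / 170 = 9.4 times the male upper limit; 1600 / 85 = 18.8 times the low limit in the same cell.

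3. **Can it be reached?** A litre of blood weighs 1040–1070 g under the assumption, so the haemoglobin alone would weigh 1600 / 1070 = 1.50 to 1600 / 1040 = 1.54 times as much as the blood containing it. The haematocrit needed would be 1600 / 380 = 4.21 to 1600 / 300 = 5.33, or about 420% to 530%. The limit cannot be reached anywhere in the assumed range.

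4. **Which unit was meant?** Read as g/L, the female pair is 85 and 160 against 90 and 170 for men: 5 g/L lower at the bottom and 10 g/L lower at the top, a coherent pattern. The female haematocrit limit points to the same scale: 0.49 × 300 = 147 g/L to 0.49 × 380 = 186 g/L, a range that contains 160 g/L. The only other conventional unit in the PCS tables is creatinine in mg/dL, and there a µmol/L value is printed beside it. The haemoglobin cell has no such pairing.

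5. **What each reading flags (illustrative female values).**

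| Haemoglobin, g/L | High limit as written (>1600 g/L) | High limit read as >160 g/L | Low limit (<85 g/L) |
|---|---|---|---|
| 80 | no | no | yes |
| 150 | no | no | no |
| 161 | no | yes | no |
| 175 | no | yes | no |
| 200 | no | yes | no |
| 250 | no | yes | no |

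The two readings differ only for women above 160 g/L. The low side is untouched.

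6. **Does haematocrit cover the gap?** Only in part. With an assumed red-cell concentration of 340 g/L, a woman at 165 g/L has a haematocrit of 165 / 340 = 48.5%. She is below the 49% limit, so neither rule would flag her as high.

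**The case against.** The best defence is that the slip may never affect a result. Data held in g/L and compared with the printed number 160 would give the rule that was presumably intended, and the SI statement in section 2.6.3 makes that more likely. This stands as a reason to moderate the claim. It does not make the text right, because the correct count would then depend on someone departing from the written unit, and a second programmer validating against the SAP could get a different answer.

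The second defence is that high values remain visible elsewhere, and this also stands. The section provides that "Abnormally low or high laboratory results based on the laboratory normal ranges will be presented in a data listing" (Listing 5.5), Listing 5.1 shows the hematology results, and Table 5.1.2 summarises hematology by visit, with minimum and maximum among the statistics in SAP section 3.1. None of these gives the PCS count, but they mean that high haemoglobin would not go unseen in the study.

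Third, nothing in either document ties these limits to a hypothesis test, stopping rule, dose change or notification. Eligibility uses separate laboratory criteria, and the protocol states: "There is no consideration for power or sample size determination in this open label study". This supports a narrow reading of the consequence.

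A reader might go further and infer that the rule can never flag a woman, that every female subject is affected, or that the study will report a false absence of findings. The documents support none of these. The low limit and the haematocrit rule still flag women. Only a woman above the intended upper limit would be missed. A false zero needs both literal coding and at least one such woman, and the documents establish neither.

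**Conclusion.** Wrong as written. The stated upper limit is 1600 g/L, ten times the same number read in g/L, and it cannot be reached. That conclusion rests on unit conversion and holds across the assumed physical ranges. The inference that g/L was intended rests on the other three haemoglobin limits and the SI rule. It is strong, but the sponsor should confirm it.

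The consequence is limited to one count in a descriptive table: women with high haemoglobin in Table 5.1.1. If the written unit is followed, that count is zero by construction. If 160 is applied to values in g/L, the count is as presumably intended. The number of women who would be missed cannot be estimated from the documents and may be none.

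**What to change.** In the hematology table of SAP section 4.5.3.1, correct the unit so that the female upper haemoglobin limit reads >160 g/L. Have the sponsor confirm that this is the intended limit, and check that the programming specification uses it, before Table 5.1.1 is produced.

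The rest of the table deserves a look in the same pass. For example, the upper haematocrit limit is lower for men (48%) than for women (49%), the reverse of the haemoglobin ordering. That may be deliberate, but it should be confirmed.

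The cost is one deleted character and a specification check. No new data and no protocol amendment are needed.

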3 STATISTICAL METHODS

3.1 General Methods

Premier Research, the designated CRO, will perform all statistical analysis using SAS version 9.4 or higher. Premier Research will be responsible for creating table, listing, and figure reports by SAS programming and delivering the reports, as well as the programs, to Supernus at study completion.

All analyses will be based on subjects who received any amount of study drug in Study 812P311. This will be referred to as the Safety Population. Since subjects received variable dosing in this study, all subject data will be summarized together under All SPN-812.

For categorical variables, summary statistics will include the number and percentage of subjects within each category (with a category for missing data). Percentages will be based on the total number of subjects with non-missing data. For continuous variables, summary statistics will include the number of non-missing observations, mean, standard deviation (SD), median, and interquartile range (Q1, Q3), minimum, maximum.

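### The upper hematocrit limit for potentially clinically significant values is lower for men (>48%) than for women (>49%), against the order of the table's other sex-specific limits, and no reason is given

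*SAP*

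**What the plan says.** The hematology table in SAP Section 4.5.3.1 sets limits by sex for two parameters only:

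- Hemoglobin: "Female: <85 g/L or >160 g/dL" and "Male: <90 g/L or >170 g/L".
- Hematocrit: "Hematocrit (Female) ≤32% or >49" percent and "Hematocrit (Male) ≤37% or >48" percent.

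No other parameter in the hematology or chemistry tables has sex-specific limits. The SAP cites no source for the limits and does not comment on the order of the hematocrit pair.

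The limits are used for counting: "The number and percentage of subjects with PCS values post-baseline will be summarized for the hematology and chemistry parameters defined in" the two tables. Repeat and extra samples count too: "All scheduled and unscheduled results will be included in this laboratory analysis". The output for hematology is Table 5.1.1. Under SAP Section 3.1 there is one reporting group: "all subject data will be summarized together under All SPN-812". Protocol Section 2.3 lists clinical safety laboratory results among the primary safety endpoints.

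**The concern.** Wherever else the table separates the sexes, the man is allowed the higher value. At the top of the hematocrit range this turns round: a man at 48.5% is flagged and a woman at 48.5% is not. The hemoglobin row, by contrast, allows men 10 g/L more than women at the high end. A single unexplained reversal of one point, in a table that also contains a unit slip, looks like a transcription error.

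The accuracy of a count in a primary safety summary is at stake. A subject enters the count with any post-baseline value beyond the limit, and the rule does not require a normal baseline. A man who sits steadily between 48% and 49% would therefore be counted. There is no comparator arm in which an excess of such flags would show up as background.

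**Working it through.** **1. Compare the four sex-specific pairs.** All inputs are from the hematology table in SAP Section 4.5.3.1.

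| Limit | Female | Male | Male minus female |
|---|---|---|---|
| Hemoglobin, low (g/L) | 85 | 90 | +5 |
| Hemoglobin, high (g/L, female unit read as g/L) | 160 | 170 | +10 |
| Hematocrit, low (%) | 32 | 37 | +5 |
| Hematocrit, high (%) | 49 | 48 | −1 |

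Three differences are positive and one is negative. The unflagged hematocrit range is 49 − 32 = 17 points wide for women and 48 − 37 = 11 points for men.

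The second row depends on reading the female upper hemoglobin limit as g/L. As printed, 160 g/dL is 1600 g/L, far above the male limit of 170 g/L. The low limit on the same line is in g/L, and SAP Section 2.6.3 states: "Values will be presented using the international system of units (SI"). The g/L reading is therefore well supported, but it does rest on correcting a separate misprint.

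**2. See what a transposition would do.** With female >48% and male >49%, the last difference becomes 49 − 48 = +1, and all four pairs run the same way. The ratio of hemoglobin to hematocrit at the upper limits moves from 160/49 = 3.27 (female) and 170/48 = 3.54 (male) to 160/48 = 3.33 and 170/49 = 3.47. The sexes come closer together. This is consistent with a transposition but does not prove one.

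**3. Count the samples that feed the table.** Protocol Sections 5.1.2 to 5.1.5 schedule hematology at Visit 3 (1), Visits 4 to 21 (18) and Visit 22 (1), and none at Visit 2. That makes 1 + 18 + 1 = 20 scheduled post-baseline samples for a subject who completes the study. Unscheduled samples (Protocol Section 5.1.7) and visits continued beyond Visit 22 (Protocol Section 3.4) can add to this; early termination reduces it.

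**4. Illustrate the size under a transposition.** Only values above 48% and up to 49% change status. The documents give no hematocrit distribution, so the means and SDs below are assumptions. For a normal distribution with mean μ and SD σ, the share of single values in the band is

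P(48 < X ≤ 49) = Φ((49 − μ)/σ) − Φ((48 − μ)/σ).

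- Men, μ = 45, σ = 3: P(X > 48) = 15.9% and P(X > 49) = 9.1%, so the band holds 6.7% (from unrounded values).
- Men, μ from 43 to 46 and σ from 2.5 to 3.5: the band holds 1.5% to 9.7%.
- Women, μ = 40, σ = 3: P(X > 48) = 0.38% and P(X > 49) = 0.13%, so the band holds 0.25%.
- Women, μ from 39 to 42 and the same σ: the band holds 0.01% to 2.1%.

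These are shares of single tests. Table 5.1.1 counts subjects, and the subjects whose high flag would change are those whose highest post-baseline value falls in the band. Turning one into the other needs the correlation between repeated values within a subject, which the documents do not give.

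**The case against.** The strongest reply is that the order of the limits proves little. PCS cut-offs are set by convention, and nothing in the SAP says that the hematocrit limits were derived from the hemoglobin limits. The printed figures suggest that they were not: at the low limits the ratio of hemoglobin to hematocrit is 85/32 = 2.66 for women and 90/37 = 2.43 for men, against 3.27 and 3.54 at the high limits. The operators at the low limit also differ (strict for hemoglobin, inclusive for hematocrit). The pattern itself is only three pairs long, and one of the three needs a unit corrected first. This much stands: the reversal is an unexplained anomaly, and a reader who infers that the hemoglobin and hematocrit rows cannot both be ordered correctly goes further than the documents allow.

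A reader might also infer that the plan over-flags men and under-flags women. That requires both limits to be wrong. If only the male limit is wrong, women are counted correctly; if only the female limit is wrong, men are.

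Finally, the reach is short. The study is descriptive, with no test or decision rule attached to this table. Change from baseline in hematology (Table 5.1.2) and the out-of-range listing based on laboratory normal ranges (Listing 5.5) do not use these cut-offs. Even under a transposition, and with male means of 44% to 46% and SD 3, 4.8% to 15.9% of male tests would still exceed 49%, so at least half of the male high flags per test would remain.

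None of this supplies a reason for the reversal, and nothing elsewhere in either document corrects it.

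**Conclusion.** The point holds as an unexplained inconsistency that should be resolved: wrong as written, of minor severity. The printed reversal is certain. That at least one of the two upper limits is wrong is a strong inference from the other three pairs, one of which relies on reading the female hemoglobin unit as g/L. A transposition is the simplest explanation but is not established, so the direction of the error stays conditional on which limit is at fault.

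Under a transposition the effect is confined to values above 48% and up to 49% and falls mainly on men. The percentages are per test and rest on assumed normal distributions; no figure per subject can be derived from the documents. If instead a single limit is wrong, the width of the affected band depends on the correct value, which the documents do not give.

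**What to change.** Before Table 5.1.1 is programmed, check both upper hematocrit limits against the source of the PCS criteria. Then either correct the table in SAP Section 4.5.3.1 so that the male upper limit is not below the female one, or state why the order is reversed. Update the Table 5.1.1 specification to match. The unit of the female upper hemoglobin limit can be corrected in the same edit.

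The cost is a small correction to one SAP table and its programming specification. Data collection and trial conduct are not affected.
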